#### 5.7.1 Withdrawal

Participants will have the right to withdraw from the study at any time without giving reason. Identifiable data already collected with consent will be retained and used in the study.

### 5.7.2 Participant transfers

If a participant moves from the area during the trial period, this will be considered a discontinuation from the study. Identifiable data already collected with consent will be retained and used in the study.

### 5.7.3 Trial closure

Trial closure will be after the last participant has returned the CGM device.

## 5.8 Sample size

We aim to recruit up to 30 participants. This is a size that the research team consider to be pragmatic and sufficient as indicative quantitative data upon which to base the sample size for a full trial.

## 5.9 Recruitment

Eligible participants will be identified and invited to participate whilst they either attend OPED or are admitted under AMU having presented with a fall or other symptoms suggestive of unrecognised hypoglycaemia.

Participant Information Sheets (PIS) will be handed out and interested patients will be consented by the research team.

No financial or non-financial incentives are offered to participants.

## 5.10 Data collection

Each participant will be given a unique trial Participant Identification Number (PIN). The preferred method of data collection is direct online entry of data by trial staff onto the central database, stored on servers based at the University of East Anglia. Data may be entered onto paper Case Record Forms (CRFs) prior to entry onto the database (but this is not essential).

Data collection, data entry and queries raised by a member of the trial team will be conducted in line with the University of East Anglia's Data Management Standard Operating Procedure.

Data for the primary outcome will be collected by downloading reports from the CGM device. This will be done through the dedicated Dexcom G6 Clarity diabetes management software (available as a free download). These reports will capture the glucose readings during the 10-day period when the CGM device was used.

The research team will also collect the following patient data through access of hospital records:

Baseline data:

- Medication use at start of study period;
- Baseline demographics and co-morbidities;
- Duration of diabetes (if available from the notes);
- HbA1c.

Follow-up data:

- ED attendances and/or hospital admissions for falls, fractures, heart attacks, ischaemic strokes and death within 30 days of removal of the participant's sensor.

Participant identification logs, screening logs and enrolment logs will be kept at the trial site in a locked cabinet within a secured room. Clinical trial team members will receive trial protocol training. Regular central monitoring will assess data quality and completeness during progression of the trial. All data will be handled in accordance with the Data Protection Act 1998.

### *5.11 Data management*

All data will be stored in a database on a secure server, provided and maintained by the University. The server environment is protected by a firewall and is patched and maintained according to best practice. The physical location of the server is protected by CCTV and security door access. Access to the database will be controlled via unique, personally attributable (i.e. not generic) usernames, password protected, and accessible only to members of the trial team, and external regulators if requested.

Data will be entered in the approved database by a member of the trial team. After completion of the trial the database will be retained on the servers of University for on-

going analysis. The identification, screening and enrolment logs, linking participant identifiable data to the pseudo-anonymized PIN, will be stored securely at the database, with access controlled on a per-user basis. Access to identifiable and pseudo-anonymized data will be stored separately within the database and permissioned accordingly. Participant contact details will be collected by a member of the research team at the time that the participant calls to express an interest in being part of the study.

### *5.12 Analysis plan*

Baseline characteristics for each participant will be presented in a Table. For categorical variables, the number and percentage will be presented. For continuous variables, the mean (and standard deviation) or median (and interquartile range) will be presented depending on the distribution.

The aim of the study is to determine if the primary outcomes can be captured, and to obtain an idea of effect sizes and their boundaries. This will inform conduct and design of future larger studies.

For participants who commenced wearing the CGM device whilst an inpatient, the research team will analyse the inpatient data separately to data captured in the community.

### *5.13 Data Monitoring*

#### *5.13.1 Data Monitoring Committee*

This study is looking into the capture of hypoglycaemic episodes through the use of CGM in older people with diabetes. It carries minimal or no risks. The device simply enables glucose concentrations to be recorded in a less invasive and more frequent manner than conventional finger-prick testing.

This study does not involve delivery of a therapeutic intervention that exerts physiological effect. The medical device has already received CE mark/approval for people with diabetes and can be purchased from the Dexcom website: (<https://www.dexcom.com/en-GB>).

Any adverse events reports will be assessed by the Independent Expert Advisor. Therefore, the trial team submit that a separate data monitoring committee is not necessary.

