A systematic review of CGM in older people found that hypoglycaemic episodes were detected in a sizeable proportion of participants, most of which were asymptomatic, with some patients spending nearly 2 hours per day in the hypoglycaemic range (2).

In a feasibility trial of CGM in 12 older people with memory problems, nine participants were insulin users, of which six (66%) were found to be affected by hypoglycaemic events (some prolonged). The average duration of hypoglycaemic events ranged from 106 minutes to 437 minutes (3). **After reviewing the CGM data with a Consultant Diabetologist, we wrote to four participants' GPs advising a change in their respective medication regimens.**

Hypoglycaemia can have devastating consequences on the lives of older people with diabetes. My research has demonstrated that hypoglycaemic episodes are associated with serious complications including heart attacks, stroke, falls, fractures, dementia and death (4, 5). Randomised trial data of intensive versus standard diabetes therapy found that rigorous lowering of glucose led to significantly more hypoglycaemia, cardiovascular events and death.

A large US study of 201705 adults with diabetes found several important factors for emergency admissions due to hypoglycaemia (6):

- age >75 years
- diabetes medications - insulin and/or sulfonylureas (SUs)
- lower annual household income
- number of comorbidities
- HbA1c at either low or high end of range.

Traditional monitoring of diabetes cannot reliably detect hypoglycaemia

**Intermittent finger-prick testing** is the traditional method of monitoring blood glucose. It requires patients to recognize impending hypoglycaemia and initiate self-testing. This can be problematic in older people because they may have:

1. Age-related physiological changes that mask symptoms of hypoglycaemia;
2. Memory problems or decline in cognition;

3. Become confused/ drowsy with hypoglycaemia and cannot test;
4. Nocturnal hypoglycaemia when asleep;
5. Age-related physical changes making it difficult to conduct testing (poor vision, arthritis).

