    - If a participant spends more than 15 minutes <3.9mmol/L (time below range), then the research team will make recommendations to adjust the medication regime to try and reduce the time spent in the hypoglycaemic range.
    - If a participant spends more than 2 ½ hours per day >13.9 mmol/L (time above range), the research team will make recommendations to adjust the medication regime to try and reduce the time spent above range.
- End of study.

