### 5.13.2 Data monitoring for harm

#### Adverse Event Definitions

|  |   |
|--|---|
| Adverse Event (AE)  | Any untoward medical occurrence in a patient or clinical trial participant administered a medicinal product and which does not necessarily have a causal relationship with this product.  |
| Adverse Reaction (AR)   | Any untoward and unintended response to an investigational medicinal product related to any dose administered   |
| Unexpected Adverse Reaction (UAR)                             | An adverse reaction, the nature or severity of which is not consistent with the applicable product information (eg Investigator's Brochure for an unauthorised product or summary of product characteristics (SPC) for an authorised product).  |
| Serious Adverse Event (SAE) or Serious Adverse Reaction (SAR) | Any AE or AR that:
results in death
is life threatening*
requires hospitalisation or prolongs existing hospitalisation**
results in persistent or significant disability or incapacity or is another important medical condition***   |
|  | 
* the term life threatening here refers to an event in which the patient is at risk of death at the time of the event; it does not refer to an event that might hypothetically cause death if it was more severe (eg a silent myocardial infarction)
 
** Hospitalisation is defined as an in-patient admission, regardless of length of stay, even if the hospitalisation is a precautionary measure for continued observation.
 
Hospitalisation for pre-existing conditions (including elective procedures that have not worsened) do not constitute an SAE
 
*** Medical judgement should be exercised in deciding whether an AE or AR is serious in other situations. Important AEs or ARs that may not be immediately life threatening or result in death or hospitalisation, but may seriously jeopardise the participant by requiring intervention to prevent one of the other outcomes listed in the table
 |

Adverse events include: pain at the insertion site of the sensor, skin reaction to the adhesive of the sensor.

All non-serious AEs and ARs, whether expected or not, should be recorded in the patient's medical notes and reported in the toxicity (symptoms) section of the Follow-up Form. SAEs and SARs should be notified immediately the investigator becomes aware of the event (in no circumstance should this notification take longer than 24 hours).

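### The case in 5.13.1 for no monitoring committee weighs only the sensor, not the medication advice in 5.3 and 5.7, and the 30-day look-up omits hospital contacts for hypo- or hyperglycaemia

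*Combined protocol and SAP*

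**What the plan says.** Section 5.13.1 says of the study: "It carries minimal or no risks". It adds: "This study does not involve delivery of a therapeutic intervention that exerts physiological effect". On safety reports it says: "Any adverse events reports will be assessed by the Independent Expert Advisor". From these statements it concludes that no separate committee is needed. The only procedure it discusses is wearing the device.

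Section 5.7 then sets out what follows the wear period. For low glucose: "If a participant spends more than 15 minutes <3.9mmol/L (time below range), then the research team will make recommendations to adjust the medication regime". For high glucose, after a threshold stated per day: "the research team will make recommendations to adjust the medication regime to try and reduce the time spent above range". The advice goes to the GP, and the next item in the timeline is the end of the study. Section 5.3 repeats the commitment, and 4.3 gives treatment adjustment as something the data should enable.

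On harm, 5.13.2 states: "Adverse events include: pain at the insertion site of the sensor, skin reaction to the adhesive of the sensor". The summary in 1.3 lists the same two kinds of event. The general definitions in 5.13.2 are written for a medicinal product, and causality is judged against a trial therapy or trial medication. No reporting period is given. Separately, 5.10 plans a hospital-record look-up to 30 days after sensor removal for a fixed list of causes. Section 5.7.3 says: "Trial closure will be after the last participant has returned the CGM device".

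**The concern.** The protocol's own background (4.1) reports randomised evidence that "rigorous lowering of glucose led to significantly more hypoglycaemia, cardiovascular events and death". A plan that cites this and also commits the team to recommending changes in glucose medication should weigh that step when it argues that risk is minimal. Section 5.13.1 does not.

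The more practical matter is what gets recorded. If treatment is changed on the team's advice, the most direct harms are a hypoglycaemic or a hyperglycaemic event that brings the participant to hospital. Neither is on the look-up list or among the named adverse events, and nothing links an event to whether advice was given or in which direction. The study is meant to inform larger ones (5.8, 5.12). Without these items it would have little to report on the safety of combining monitoring with advice.

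**Working it through.** The only design figure in the plan is the target of up to 30 participants (5.8). It is described as pragmatic, with no calculation to reproduce, and the point does not depend on it. The main check is to set the passages side by side.

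**What each route would catch after the advice**

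| Event | Look-up list (5.10) | Named AE (1.3, 5.13.2) | SAE definition (5.13.2) |
|---|---|---|---|
| Death | Yes | No | Yes |
| Admission for fall, fracture, ischaemic stroke or heart attack | Yes | No | Yes |
| Admission for hypo- or hyperglycaemia | No | No | Yes, if the reporting period extends that far |
| ED-only attendance for hypo- or hyperglycaemia | No | No | Only if another seriousness criterion is met |
| Glycaemic harm without hospital contact | No | No | Only if another seriousness criterion is met |

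The SAE column is generous: the parent definition refers to a medicinal product, and relatedness is judged against a therapy this study does not have.

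**Timing**

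- Participation lasts 10 to 14 days from consent (5.7). If the sensor comes off on day 10 to 14, the look-up ends on day 10 + 30 = 40 to day 14 + 30 = 44.
- Section 5.7 has the sensor removed and the equipment collected at one visit. For the last participant, closure under 5.7.3 therefore falls 30 days before the look-up ends. Reporting duties in that interval are not defined.
- The lag L from sensor removal to any medication change is not stated. The look-up covers 30 − L days after the change. With assumed lags of 7, 14 and 21 days, that is 23, 16 and 9 days.

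**Scale (illustration only)**

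- Section 4.1 reports that 4 of 12 participants in the feasibility trial had letters advising a change: 4/12 = 33.3%.
- Clopper-Pearson limits: lower = Beta quantile(0.025; 4, 9) = 9.9%; upper = Beta quantile(0.975; 5, 8) = 65.1%.
- Applied to 30: 30 × 0.333 = 10; 30 × 0.099 = 3.0; 30 × 0.651 = 19.5. That is about 10, with limits of about 3 and 20.
- The documents give no risk of an advice-related event. If it were 5% to 10% per advised participant (an assumption), the chance of at least one is 1 − (1 − p)^m. For m = 10 this is 40% to 65%; for m = 3, 14% to 27%; for m = 20, 64% to 88%. The expected count at m = 10 is 0.5 to 1, so any listing can only be descriptive.

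The advice rate cannot be derived from the protocol's own rule. The low-glucose trigger in 5.7 has no time base, while the high-glucose trigger is per day. The authors should reconcile this.

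**The case against.** The case on the other side is substantial, and most of it stands.

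- **Delivery.** A reader might infer that 5.13.1 is flatly contradicted by 5.7. It is not. The team recommends and the usual clinicians decide. Sections 4.4, 5.3 and 5.5 keep diabetes management as it is while the study runs.
- **Follow-up exists.** A reader might infer that the consequences of the advice go unmonitored. The documents do not support that: the look-up starts at sensor removal, around when routine advice is issued, and records death and the main cardiovascular events along with falls and fractures.
- **Open list.** The adverse-event list in 5.13.2 is not closed, and any in-patient admission can qualify as serious. A glycaemic admission is unnamed but not excluded.
- **The advisor.** A reader might infer that the Independent Expert Advisor never sees what follows the advice. Section 5.15 gives the advisor oversight of participants' interests, and 6.9 gives access to the final dataset.
- **Timing of advice.** A reader might infer that all advice comes after the sensor is off. Readings are unblinded and 5.3 provides a helpline, so the team may also make recommendations during wear.
- **The 4 of 12.** These were people with memory problems, nine of them insulin users. Section 4.1 does not say that the same triggers applied or which way the advice went. The interval reflects sampling error only.
- **Attribution.** In up to 30 uncontrolled participants aged 75 or over, selected for falls or similar symptoms, an event can rarely be attributed to the advice.

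These arguments narrow the point but do not remove it. The cause list in 5.10 is fixed and omits glycaemic contacts, the dataset open to the advisor contains only what is collected, and an open adverse-event list helps little without a stated window or a relevant causality reference.

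**Conclusion.** The point holds as a gap in reasoning and in capture. The argument for minimal risk leaves out a step that the protocol itself commits to. Safety capture misses hospital contacts for hypoglycaemia and hyperglycaemia, has no stated window, and judges causality against a therapy that the study does not give.

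The number affected is uncertain. About 10 of 30 advised, within about 3 to 20, assumes that the feasibility rate carries over from a different population, and says nothing about how many would be harmed. No primary outcome or planned analysis is affected.

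A reader might infer that a monitoring committee is required. The documents do not support that: the study is small, the treating clinicians decide on treatment, and an independent advisor is in place. The change is worth making because it adds the most relevant events to a look-up that is already planned.

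**What to change.** 1. **Sections 5.10 and 5.6:** add ED attendances and admissions for hypoglycaemia and for hyperglycaemia to the 30-day look-up and the secondary outcome, with the same starting point (sensor removal) in both places.
2. **Section 5.13.2:** state that SAE capture runs from sensor fitting to 30 days after removal. In-patient admissions count as SAEs, and ED-only attendances are recorded as events. Assess relatedness to study procedures, including the advice. Bring 5.7 and 5.7.3 into line with that window.
3. **Independent Expert Advisor:** provide a short listing of these events showing whether advice was given, whether during or after wear, and in which direction. Label it descriptive.
4. **Section 5.13.1:** confine the statement about therapeutic intervention to the device, and acknowledge the recommendations.

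Items 1 and 2 change what is collected; item 4 alone would be only drafting. The cost is two added causes on an existing look-up, a few more SAE forms and one listing, with no new visits or participants. Glycaemic harm that never reaches hospital, and events beyond 30 days, would still largely be missed, and the report should say so. No clinical rule is proposed.

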### 5.13.2 Data monitoring for harm

#### Adverse Event Definitions

|  |   |
|--|---|
| Adverse Event (AE)  | Any untoward medical occurrence in a patient or clinical trial participant administered a medicinal product and which does not necessarily have a causal relationship with this product.  |
| Adverse Reaction (AR)   | Any untoward and unintended response to an investigational medicinal product related to any dose administered   |
| Unexpected Adverse Reaction (UAR)                             | An adverse reaction, the nature or severity of which is not consistent with the applicable product information (eg Investigator's Brochure for an unauthorised product or summary of product characteristics (SPC) for an authorised product).  |
| Serious Adverse Event (SAE) or Serious Adverse Reaction (SAR) | Any AE or AR that:
results in death
is life threatening*
requires hospitalisation or prolongs existing hospitalisation**
results in persistent or significant disability or incapacity or is another important medical condition***   |
|  | 
* the term life threatening here refers to an event in which the patient is at risk of death at the time of the event; it does not refer to an event that might hypothetically cause death if it was more severe (eg a silent myocardial infarction)
 
** Hospitalisation is defined as an in-patient admission, regardless of length of stay, even if the hospitalisation is a precautionary measure for continued observation.
 
Hospitalisation for pre-existing conditions (including elective procedures that have not worsened) do not constitute an SAE
 
*** Medical judgement should be exercised in deciding whether an AE or AR is serious in other situations. Important AEs or ARs that may not be immediately life threatening or result in death or hospitalisation, but may seriously jeopardise the participant by requiring intervention to prevent one of the other outcomes listed in the table
 |

Adverse events include: pain at the insertion site of the sensor, skin reaction to the adhesive of the sensor.

All non-serious AEs and ARs, whether expected or not, should be recorded in the patient's medical notes and reported in the toxicity (symptoms) section of the Follow-up Form. SAEs and SARs should be notified immediately the investigator becomes aware of the event (in no circumstance should this notification take longer than 24 hours).

When an AE or AR occurs, the investigator responsible for the care of the participant must first assess whether or not the event is serious using the definition given in Table 1. If the event is classified as 'serious' then an SAE form must be completed and notification sent within one working day.

The investigator must assess the causality of all serious events or reactions in relation to the trial therapy using the definitions below.

#### Causality definitions

| Relationship           | Description   | Event type    |
|------------------------|---|---------------|
| Unrelated              | There is no evidence of any causal relationship   | Unrelated SAE |
| Unlikely to be related | There is little evidence to suggest that there is a causal relationship (eg the event did not occur within a reasonable time after administration of the trial medication). There is another reasonable explanation for the event (eg the participant's clinical condition or other concomitant treatment)      | Unrelated SAE |
| Possibly related       | There is some evidence to suggest a causal relationship (eg because the event occurs within a reasonable time after administration of the trial medication). However, the influence of other factors may have contributed to the event (eg the participant's clinical condition or other concomitant treatment) | SAR           |
| Probably related       | There is evidence to suggest a causal relationship and the influence of other factors is unlikely   | SAR           |
| Definitely related     | There is clear evidence to suggest a causal relationship and other possible contributing factors can be ruled out.  | SAR           |

